#### 7.2.3 Sensitivity analyses

In the primary analysis, individuals are excluded if they did not receive iron supplementation at enrolment but received it during follow-up due to changes in ferritin or haemoglobin values. Sensitivity analyses will be conducted for the primary outcome by including those requiring iron supplementation during follow-up in the control group.

Since the treatment is not assigned at random there is a strong potential that confounders will introduce bias into the estimates of the treatment effects. As an attempt to remedy this, sensitivity analyses using inverse probability weighting will be conducted for the primary outcome and the secondary outcomes that relate to efficacy. If we use  $X_i$  to represent group membership for participant  $i$  and  $Z_i$  is a vector of predictors for this participant, the first step of the analysis is to estimate the stabilized inverse probability of "treatment" weights  $W_i$  for subject  $i$ ,  $W_i = P(X_i = x_i)/P(X_i = x_i|Z_i)$ . The predictors  $Z_i$  include age, sex, screening haemoglobin concentration, screening plasma ferritin concentration, socio-economic status, medical history, and diet. An estimate of  $P(X_i = x_i|Z_i)$  can be obtained by logistic regression

and  $P(X_i = x_i)$  can be estimated by the sample proportion. One then uses these weights in a regression model to adjust for participant characteristics that differ between the groups.

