Analytical approaches to the analysis of data from the prevalence study will focus on univariate summaries but will also investigate risk factors for deferral, ID, and IDA. Exact confidence intervals for the probability of deferral, the probability of ID and the probability of IDA will be computed using the method first described by Clopper and Pearson. Logistic regression will be used to assess risk factors for these outcomes. For deferral, these risk factors will include age and sex but likely little else as the data we can obtain for these individuals is limited. For ID and IDA, the role of demographics will be investigated as well as other factors including socio-economic status, medical history, and diet. Final models for the impact of risk factors on deferral, ID, and IDA will include demographics and a selection of covariates found to have a statistically significant univariate association with each of these outcomes.

The analysis for the primary outcome of haemoglobin levels at 4 months will be conducted using a linear model with haemoglobin levels at 4 months as the response variable. It is unlikely that there is a need to transform the response variable as haemoglobin levels are usually symmetrically distributed with tails that decay at rates consistent with the normal distribution. However, if informal univariate assessments of normality (e.g., qq-plots) indicate strong departures from these expectations, the Box-Cox transformation will be used to select a transformation. The set of explanatory variables will be group membership (i.e.,

received iron supplementation or not), baseline haemoglobin, sex, and age. A 1-sided t-test for the regression coefficient associated with group membership will be conducted with a significance level of 0.025 to test the inferiority hypothesis. This analysis will exclude individuals who did not receive iron supplementation at baseline but received it during follow-up due to changes in ferritin or haemoglobin values. The frequency of this will be closely tracked and if more than 10% of participants in the group initially not receiving iron supplementation receive iron supplementation during follow-up, alternative analysis approaches will be considered and presented to the DSMB. At a minimum, sensitivity analyses which include those requiring iron supplementation during follow-up will be pursued. These analyses will include those requiring supplementation during follow-up in each of the 2 groups.

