Parallel groups' trial to assess the acceptability of iron supplementation: Using a non-inferiority design with a non-inferiority margin of 1 g/dL for haemoglobin levels at 4 months, a 1-sided alpha level of 0.025, at least 85% power and under the assumption that the true difference in the means is 0.3 requires 262 participants (131 per arm). This number has been increased to allow up to 10% loss to follow-up or iron supplementation for those initially not requiring supplements (such individuals will be excluded from the primary analysis: see Section 7.2.1 for further details), thus the sample size is 292. For efficiency, participants will be enrolled into both parts of the quantitative study.

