## 4 Administration of Study Treatment

Potential first-time donors will be asked if they are interested in participating in a study of the prevalence of ID and IDA and the impact of iron supplementation on haemoglobin levels and repeat donation. Those who express interest, consent to the study, and are eligible will be asked to return within 3 weeks. During this 3-week period a FBC, a peripheral blood film analysis, and a plasma ferritin measurement will be conducted, and participants will be classified as iron supplement participants (e.g., anaemic, ID, IDA) or otherwise (which we refer to as controls in this protocol).

Those found to be anaemic, ID or IDA will receive oral iron supplementation and nutritional counselling. The oral iron supplements will be ferrous sulphate 200mg (65mg Elemental iron). The iron supplements are already available at the Korle-Bu Teaching Hospital Pharmacy. The study principal investigators and study pharmacist will ensure the medicine is stored properly and dispensed only when needed for study participants. The following will be monitored and completed on a periodic basis to ensure the medicine is within study guidelines, pharmaceutical compliance, and manufacturer guidelines:

Drug Accountability Record.

Iron supplement Safety and Handling Sheet.

Controls will not be given iron supplementation at enrolment but will receive the standard practice of nutritional counselling for blood donors. If someone not given iron supplements at enrolment is found to be anaemic, ID or IDA at a follow-up visit that individual will receive iron supplements.

All study participants will have nutritional counselling, dietary advice, and for those

receiving iron, the need for iron therapy to be used consistently 3 days a week.

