## 7.2 Parallel group trial

**Analysis cohort:** The intervention group is the group assigned oral iron supplementation at enrolment and the control group consists of those not assigned oral iron supplementation at enrolment.

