#### Primary analysis

The analysis for the primary outcome of haemoglobin levels at 4 months will be conducted using a linear model with haemoglobin levels at 4 months as the response variable. It is unlikely that there is a need to transform the response variable as haemoglobin levels are usually symmetrically distributed with tails that decay at rates consistent with the normal distribution. However, if informal univariate assessments of normality (e.g., qq-plots) indicate strong departures from these expectations, the Box-Cox transformation will be used to select a transformation. The set of explanatory variables will be group membership (i.e., received iron supplementation at enrolment or not), screening haemoglobin, sex, and age. A 1-sided t-test for the regression coefficient associated with group membership will be conducted with a significance level of 0.025 to test the inferiority hypothesis. This analysis will exclude individuals who did not receive iron supplementation at enrolment but received it during follow-up due to changes in ferritin or haemoglobin values. The frequency of this will be closely tracked and if more than 10% of participants in the group initially not receiving iron supplementation receive iron supplementation during follow-up, alternative analysis approaches will be considered and presented to the DSMB.

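### SAP 7.2.3 omits the iron-group placement of controls who start iron, which the protocol specifies, so the effect of excluding them is not bracketed

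*SAP*

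**What the plan says.** Both documents handle these participants in the same way in the primary analysis. SAP 7.2.1 states that it will "exclude individuals who did not receive iron supplementation at enrolment but received it during follow-up due to changes in ferritin or haemoglobin values". The trigger is in SAP section 4: "If someone not given iron supplements at enrolment is found to be anaemic, ID or IDA at a follow-up visit", that person is given iron. Both documents also set a threshold: "if more than 10% of participants in the group initially not receiving iron supplementation receive iron supplementation during follow-up", other analysis approaches are to be considered and taken to the DSMB.

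They part on the sensitivity analysis. The protocol (Data Analysis, Quantitative Data Analysis) continues after the threshold: "At a minimum, sensitivity analyses which include those requiring iron supplementation during follow-up will be pursued". It then says where these people go: "These analyses will include those requiring supplementation during follow-up in each of the 2 groups".

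SAP 7.2.3 plans the sensitivity analysis of the primary outcome "by including those requiring iron supplementation during follow-up in the control group". It names no second placement, and the threshold clause in SAP 7.2.1 does not supply one.

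**The concern.** Only controls can newly start iron, so the protocol's reference to each of the two groups is most sensibly read as two placements: once as controls, once as iron recipients. The SAP carries over one of them.

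The exclusion rests on ferritin or Hb measured after enrolment, and Hb is also the outcome, so it needs testing from both sides. A control who starts iron because Hb fell will probably still be low at 4 months, above all if the fall is first found at that visit. Returning such people to the control group lowers the control mean and favours non-inferiority. Counting them in the iron group pulls the other way. With only the first, a positive primary result could be reported as supported by a sensitivity analysis that, in that situation, could only have agreed with it.

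**Working it through.** **Design figures.** SAP 2.4 gives margin 1.0 g/dL, SD 1.89, true difference -0.3, and "a 1-sided alpha level of 0.025, at least 85% power" appears under Sample size in SAP 1.2. Then n = 2 × 1.89² × (1.960 + 1.036)² / (1 - 0.3)² = 130.9, so 131 per arm, and 262 / 0.9 = 291.1, raised to 292 (146 per arm). The plan's figures reproduce and are not in dispute.

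**Formulas.** Take n per arm at enrolment, with k of the n controls starting iron. Let D be the iron-minus-control difference after exclusion, and g the amount by which the starters' mean 4-month Hb lies below that of other controls.

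- Control placement: D + (k/n)g
- Iron placement: (nD - kg)/(n + k)
- 95% half-width: 1.96 × 1.89 × √(1/n_iron + 1/n_control)

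The documents give neither k nor g. The values below are assumptions: n = 131, k = 13 or 26 (about 10% or 20%), g = 0.8 or 1.2.

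- Control placement, k = 13, g = 0.8: -0.30 + (13/131)(0.8) = -0.22
- Control placement, k = 26, g = 1.2: -0.30 + (26/131)(1.2) = -0.06
- Iron placement, k = 13, g = 0.8: (-39.3 - 10.4)/144 = -0.35
- Iron placement, k = 26, g = 1.2: (-39.3 - 31.2)/157 = -0.45

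Estimates, with 95% lower bounds in brackets:

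| D, k, g | Exclusion (primary) | Control group | Iron group |
|---|---|---|---|
| -0.30, 13, 0.8 | -0.30 (-0.77) | -0.22 (-0.68) | -0.35 (-0.81) |
| -0.30, 26, 1.2 | -0.30 (-0.79) | -0.06 (-0.52) | -0.45 (-0.92) |
| -0.45, 26, 1.2 | -0.45 (-0.94) | -0.21 (-0.67) | -0.57 (-1.04) |

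In the first two rows all three analyses show non-inferiority. In the third the primary analysis passes, the retained placement passes easily, and the omitted one fails.

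**Where the order reverses.** Setting the two placements equal gives g = -Dn/(2n + k). With n = 146 and k = 15 or 29, break-even is about 0.14 g/dL at D = -0.3 and 0.46-0.48 g/dL at D = -1.0. Above it, control placement is the easier test; below it, iron placement is. Iron placement falls below the primary estimate only when g exceeds -D, that is 0.30 g/dL at D = -0.3.

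On the margin calculation in SAP 1.2, non-deferred men average 14.5 g/dL against a threshold of 13 (women 13.0 against 11.5). A control triggered by low Hb is thus at least 1.5 g/dL below that mean when detected. No such deficit follows for a control triggered by ferritin alone.

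**Chance of showing non-inferiority** (146 per arm, k = 15, D = -0.3, normal approximation):

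| g | Exclusion | Control group | Iron group |
|---|---|---|---|
| 0 | 87% | 89% | 91% |
| 1.0 | 87% | 95% | 81% |
| 1.5 | 87% | 97% | 75% |

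**Check with adjustment.** The planned model adjusts for screening Hb, sex and age. A small simulation adjusting for baseline Hb only assumed men only, groups cut at 13 g/dL, correlation 0.7, an adjusted difference of -0.3, and the 10% of controls with the lowest follow-up Hb starting iron. With no response to iron, control placement gave -0.30 (non-inferiority shown in 73%) and iron placement -1.19 (under 1%). With an assumed 2 g/dL response the order reversed: -0.72 (21%) against -0.58 (42%).

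**The case against.** The strongest reply is that the retained analysis is the principled one. SAP 7.2 says "the control group consists of those not assigned oral iron supplementation at enrolment", so control placement analyses people by their group at enrolment. Iron placement reclassifies them on a later result. With visits at 2, 4 and 6 months, those found deficient at month 4 or 6 had no study iron before the 4-month measurement, and month-2 starters had about half the course. This stands: control placement is legitimate, and iron placement is a crude stress test. It is still one the protocol says will be done.

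The protocol text can also be called softer than a commitment. It describes itself as a summary ahead of a detailed SAP, and the minimum requirement follows the 10% sentence, so it may apply only above that threshold. Even then the SAP does not provide the second placement. The SAP's table of changes is not in the supplied text, so a stated reason cannot be ruled out.

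A reader might infer that the SAP kept whichever placement makes non-inferiority easier. The documents do not support that as fact. The direction depends on unseen 4-month Hb, low ferritin alone can trigger iron, and a good response from month 2 can reverse the order. Nothing in the text points to a motive.

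A reader might also infer that the primary test has become lenient. It has not: the omission leaves it untouched, and if starters have lower Hb, excluding them is stricter than returning them to the control group.

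**Conclusion.** The mismatch is plain on the text: the protocol specifies two placements and the SAP keeps one. The consequence is conditional. With a clear 4-month Hb deficit among controls who start iron (likely when low Hb is the trigger, uncertain for ferritin alone or for iron taken from month 2), the retained analysis cannot overturn a positive primary result. With little or no deficit it can be the harder of the two. Either way, a single placement does not show the range over which the exclusion could matter.

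The size is modest. In the assumed range of 10-20% starters, 0.8-1.2 g/dL lower, with -0.30 after exclusion, the placements differ by 0.13 to 0.39 g/dL (-0.22 to -0.35; -0.06 to -0.45) and no conclusion changes. At -0.45 after exclusion, with 20% starters 1.2 g/dL lower, it does. These figures are unadjusted, use a common SD of 1.89 and ignore other loss to follow-up. It would go too far to say that the trial's non-inferiority claim is unsafe.

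**What to change.** In SAP 7.2.3, specify two sensitivity analyses of the primary outcome, each using the primary model: controls who started iron during follow-up are included (a) in the control group and (b) in the iron group. Report both beside the primary analysis, with the number of starters, and state whether the non-inferiority conclusion agrees across all three. A formal rule requiring success in both is not needed and appears in neither document. If the iron-group placement was dropped on purpose, give the reason in the SAP instead.

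The cost is one extra model run and a sentence or two. SAP 1.1 allows updates until it is finalised before database lock.

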Anaemia is a state in which the amount of red blood cells (RBCs) is insufficient to meet the body's physiologic needs ²⁴. Mild anaemia is defined as Hb ranging from 11-12.9 g/dL in adult males and 11-11.9 g/dL in adult females. Moderate anaemia is defined as Hb level of 8-10.9 g/dL and severe anaemia is defined as Hb level of less than 8 g/dL for all the age groups ^{25,26}.

Following FBC and plasma ferritin estimation, screened participants will be classified by the WHO criteria as shown in Table 4:

Table 4: Definition of Iron Status Criteria

| Haemoglobin concentration, g/dL | Plasma ferritin concentration µg/L | Interpretation |
|--|------------------------------------|---|
| [Male] >13.0 [Female] >11.5 | < 15 | Iron deficiency without anaemia |
| [Male] ≥8.0-13.0 [Female] ≥8.0-11.5 | < 15 | Iron deficiency with mild to moderate anaemia |

| | | | |
|-------|------|------|-------------------------------------|
| [All] | <8.0 | < 15 | Iron deficiency with severe anaemia |
|-------|------|------|-------------------------------------|

Schedule of Assessments (Table 5)

| Assessment | Screening (Day -14 to 0) | Enrolment (Day 0) | Biweekly (Throughout) | Interim Visit 1 | Interim Visit (Week 8-10) | Interim Visit 2 | Final Visit (Week 24) |
|--|-----------------------------|----------------------|--------------------------|--------------------|------------------------------|--------------------|--------------------------|
| NBSG Pre-Donation Assessment | X | | | | | | X |
| Informed Consent | X | | | | | | |
| Inclusion and Exclusion Criteria | X | | | | | | |
| Demographics | X | | | | | | |
| Full Blood Count and peripheral blood comment | X | | | X | X | X | |
| Plasma Ferritin | X | | | X | X | X | |
| Malaria Parasites Testing (RDT) | X | X | | X | X | X | |
| Nutritional Counselling | | X | | X | X | X | |
| Qualitative Assessment | | | | | | | X |
| Follow-Up Calls | | | X | | | | |
| Return Blood Donation Status | | | | X | X | X | X |
| Assessment for Adverse Events | | X | X | X | X | X | X |
| Adherence Assessment (for those receiving supplemental iron) | | | X | X | X | X | X |
| RDT – Rapid Diagnostic Test | | | | | | | |

Enrolment

Participants will be re-assessed with their laboratory results at the Day 0 visit.

- ***Eligibility Check***

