The parallel group's component is designed as a non-inferiority trial for haemoglobin levels at 4 months. At baseline, the 2 groups will be determined based on the need for iron supplementation: all individuals with ID, IDA or low haemoglobin (gender specific values), who satisfy our eligibility criteria regardless of deferral status, will receive iron supplements while all others will not. While a high prevalence of ID and IDA is expected, enrolment will be staggered so that an equal number of participants from each group are enrolled from each site with at least 1 participant who is assigned to iron supplementation. If there are more potential participants in one group at some site, randomization will be used to select the individuals to enroll in the trial to maintain balance over time. The extent of adherence is a central question for this study, and it is also unclear if the haemoglobin deficiency can be improved above what is seen in the control group, hence it is not hypothesized that those receiving iron supplementation will have higher levels of haemoglobin at 4 months. The hypothesis about the iron supplementation intervention is that it will improve haemoglobin levels to near that seen among those who did not receive iron supplementation. If haemoglobin levels are higher in those receiving iron supplementation the intervention would also be deemed a success. Hence a non-inferiority trial is most appropriate for this hypothesis.

Selection of the margin is a critical component of a non-inferiority trial. Here, we specify a margin of 1 g/dL for haemoglobin levels at 4 months. Under a collection of reasonable assumptions, this margin will ensure that the majority of those with low haemoglobin at screening will have haemoglobin levels at 4 months above the threshold for anaemia and should therefore qualify as donors. To see this, assume that half of donors are anaemic at screening (using the thresholds for anaemia of 13 g/dL for men and 11.5 g/dL for women). A simple calculation finds that if we assume haemoglobin levels are normally distributed (which is a reasonable assumption based on observed distributions for haemoglobin in unselected individuals in West Africa) and the standard deviation of screening haemoglobin levels is 1.89 g/dL (this estimate will be described below) then the mean haemoglobin level among men who are deferred is 11.5 g/dL and the mean haemoglobin level among men who are not deferred is 14.5 g/dL (these values for

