### 2.2 Randomization

There is no randomization in the cross-sectional component. In the parallel groups' component, the 2 groups will be determined based on the need for iron supplementation, so the treatment is not assigned by randomization.

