### Secondary analyses of secondary outcomes related to efficacy

The first two secondary outcomes that related to efficacy (i.e., change in haemoglobin over 4 months and ferritin levels at 4 months) will be treated as continuous variables and will serve as response variables in multiple regression models. It is anticipated that there will not be a need to transform the change in haemoglobin (however the Box-Cox transformation will be pursued if there is evidence for skewness), but it is anticipated that ferritin will need to be transformed. Usually logarithmic transformations are required to reduce the skewness of variables of this sort (i.e., measured by an ELISA), and this will be pursued, but other transformations may be more appropriate. The multiple regression models will include group membership, screening haemoglobin, screening ferritin (log transformed if substantial skewness is present), sex, and age. The remaining 3 outcomes that related to efficacy (i.e., diagnosis of ID or IDA at 4 months, attempt to return for donation within 6 months, and successful donation within 6 months) will be examined using logistic regression models with group membership, screening haemoglobin, screening ferritin (perhaps transformed), sex, and age as covariates. A significance level of 5% will be used to determine statistical significance of effects and 95% confidence intervals will be used to summarize effect sizes.

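### The weights in SAP 7.2.3 are built from the variables that fix the arm, so they cannot jointly balance screening haemoglobin and ferritin, and the weighted outcome model is not named

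*SAP*

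**What the plan says.** SAP 2.2 states that "the 2 groups will be determined based on the need for iron supplementation, so the treatment is not assigned by randomization". SAP 1.2 (Design) gives the rule: "all individuals with ID, IDA or low haemoglobin (gender specific values), who satisfy our eligibility criteria regardless of deferral status, will receive iron supplements", and everyone else receives none. SAP 4 repeats it: "Those found to be anaemic, ID or IDA will receive oral iron supplementation and nutritional counselling". SAP 1.2 also says that blood is not normally drawn at the enrolment visit, so the screening sample sets the group. The Protocol supplies the iron-deficiency (ID) cut-off: "Following FBC and plasma ferritin estimation, screened participants will be classified by the WHO criteria as shown in Table 4", and that table and the Treatment text use ferritin below 15 µg/L.

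SAP 7.2.3 acknowledges that confounding is likely and offers stabilised inverse probability weights as a sensitivity analysis. The predictors Z "include age, sex, screening haemoglobin concentration, screening plasma ferritin concentration, socio-economic status, medical history, and diet". The outcome model is described only in this sentence: "One then uses these weights in a regression model to adjust for participant characteristics that differ between the groups".

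The unweighted models are specified elsewhere. The primary model (SAP 7.2.1) contains "group membership (i.e., received iron supplementation at enrolment or not), screening haemoglobin, sex, and age", without ferritin. For the continuous secondary efficacy outcomes (SAP 7.2.2), "The multiple regression models will include group membership, screening haemoglobin, screening ferritin (log transformed if substantial skewness is present), sex, and age". The logistic models for the other efficacy outcomes also contain ferritin.

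**The concern.** Inverse probability weighting needs every kind of participant, as described by Z, to have some chance of being in either group. Here Z contains the three variables that decide the group. The analysis offered as the answer to confounding therefore cannot work for the two largest known differences between the arms.

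The failure may not show. Fitted with main effects, the logistic model will often converge and produce weights. SAP 7.2.3 asks for no check of overlap, balance or extreme weights. A reader of the results could take a weighted estimate close to the primary one as evidence that confounding has been handled.

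Because the weighted outcome model is not named, it is also unclear whether ferritin is adjusted for. The primary model omits it and the secondary models include it.

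**Working it through.** **1. Numbers per arm.** Inputs from SAP 2.4: margin 1.0 g/dL, SD 1.89 g/dL, true difference -0.3 g/dL, one-sided alpha 0.025, power 85%.

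n per arm = 2 × 1.89² × (1.960 + 1.036)² / (1.0 - 0.3)² = 7.144 × 8.978 / 0.49 = 130.9, so 131 per arm and 262 in total. Then 262 / 0.9 = 291.1, so 292, or 146 per arm. This agrees with the SAP, and 146 per arm is used below.

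**2. Overlap under the SAP rule.** This step needs no simulation.

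| Screening result | Iron | Control |
|---|---|---|
| Hb not low, ferritin ≥15 | none | all |
| Hb not low, ferritin <15 | all | none |
| Hb low, ferritin ≥15 | all | none |
| Hb low, ferritin <15 | all | none |

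Every row has an empty cell, so P(iron | Hb, ferritin, sex) is 0 or 1. Iron participants with control-like Hb all have ferritin below 15, and those with control-like ferritin all have low Hb. Up-weighting one set to improve balance on one variable worsens it on the other.

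**3. Why software may not object.** The iron region is L-shaped in Hb and ferritin, so a main-effects logistic model usually cannot separate it from the control region and returns probabilities strictly between 0 and 1. A model coded with the rule's own indicators (low Hb, ferritin <15) separates completely and cannot be fitted.

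**4. The Protocol's rule.** Protocol Design and Treatment assign iron for ID or iron deficiency anaemia (IDA) only. Ferritin alone then separates the arms. The fitted probability of the observed group goes to 1, each stabilised weight becomes 0.5 / 1 = 0.5, and constant weights remove no imbalance.

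**5. Illustrative size under the SAP rule, true effect zero.**
- From the documents: Hb SD 1.89 g/dL; anaemia 48%; Hb cut-offs 13 / 11.5 g/dL; ferritin cut-off 15; Hb ≥10 g/dL for entry.
- Assumed: log-normal ferritin with log-SD 0.9; Hb-ferritin correlation 0.65; 70% men; slope of month-4 on screening Hb 0.7.
- Two scenarios for ferritin <15: 41.3% / 68.8%. The first is 48% × 86.1% from SAP 2.4, which is strictly the share who are anaemic with ID. The second comes from a different unpublished study in the Protocol's Problem Statement. Both are illustrative.

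| Quantity | 41.3% | 68.8% |
|---|---|---|
| Iron-arm effective sample size, of 146 | about 20 | about 6 |
| Screening-Hb gap, unweighted (g/dL) | -2.25 | -2.08 |
| Screening-Hb gap, weighted (g/dL) | about -1.1 | about -1.8 |
| SD of estimate, weighted with Hb, sex, age | about 0.45 | about 0.50 |
| SD of estimate, primary model | about 0.22 | about 0.22 |

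The variance ratio is (0.45 / 0.22)² = 4.2 and (0.50 / 0.22)² = 5.2.

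Varying the assumed correlation from 0.3 to 0.8 gives effective sizes of 19-25 / 5-6 and remaining Hb gaps of 0.7-1.5 / 1.4-2.0 g/dL. A separate set of assumed Hb and ferritin distributions gave effective sizes of about 2 to 36. In none of its scenarios were Hb and log ferritin both within 0.1 standardised difference.

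**6. If ferritin itself affects month-4 Hb** (assumed 0.6 g/dL per log unit), the biases are:
- Primary model: about -0.5 / -0.65 g/dL.
- Weighted model with Hb, sex and age: about -0.4 / -0.25 g/dL.
- Unweighted model adding log ferritin: about zero if the relation is linear, with SD about 0.26.

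If the true relation is instead a 0.5 g/dL step at ferritin 15 (assumed), the last model is biased by about -0.23 / -0.40 g/dL.

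**The case against.** The strongest reply is that this is one sensitivity analysis in a pilot, that the SAP itself presents it only as an attempt, and that the natural reading of the unnamed regression model is the SAP 7.2.1 model with weights. On that reading, if ferritin has no effect of its own, the weighted estimate is close to unbiased and merely imprecise. If ferritin does matter, the weighted estimate is less biased than the primary one in these illustrations. All of that stands, and it limits the point to what the weighting can claim and how precise it is.

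A reader might infer that the weighted result would be badly biased under no effect. That requires a weighted model containing group alone. No efficacy model in SAP 7.2.1 or 7.2.2 has that form, and the sign of the resulting bias changes with the assumed distributions. The documents do not support that reading.

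A second reply is that dropping Hb and ferritin from Z would rescue the weighting. It would give stable weights, but with nothing left to do. Once Hb, ferritin and sex are in the outcome model, no other predictor can be associated with group, because those three already fix it. With an assumed diet item, the unweighted ferritin-adjusted model gave 0.00 against +0.02 / +0.05 g/dL with such weights. The gain comes from having ferritin in the outcome model.

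**Conclusion.** Wrong as written, limited to the weighted analysis in SAP 7.2.3. That the weights cannot jointly balance Hb and ferritin follows from the assignment rule and the list of predictors, under either the SAP or the Protocol rule, and rests on no simulation. The sizes (effective sample about 20 / 6 of 146, remaining Hb gap about 1.1 / 1.8 g/dL, variance roughly four to five times that of the primary model) apply to the SAP rule only. They depend on Hb and ferritin distributions that the documents do not give.

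A reader might also infer that the primary non-inferiority test or the sample size is invalidated. Neither uses these weights, and both are unchanged by this point. The bias figures for the primary model depend on an assumed ferritin effect and show why a ferritin-adjusted sensitivity analysis is useful. They are not estimates of what will happen in this trial.

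**What to change.** In SAP 7.2.3, replace the weighting with the following:

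- For the primary outcome, an unweighted linear sensitivity model containing group, screening Hb, screening ferritin (log transformed if skewed), sex and age, plus named items for socio-economic status, medical history and diet.
- For the secondary efficacy outcomes, the SAP 7.2.2 models, which already contain ferritin, with the same items added.
- A statement that the arms do not overlap on Hb and ferritin jointly, so control of these two rests on the assumed form of the outcome model.

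If weighting is kept at all, leave screening Hb and ferritin out of Z, put both in the outcome model, and do not claim that the weights remove confounding. The primary model in SAP 7.2.1 stays as it is.

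The Protocol (Design, Treatment) assigns iron for ID or IDA, while the SAP (1.2 Design, 4) also includes low Hb. These sections must be reconciled.

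Cost: SAP wording only, with no new data. SAP 1.1 allows updates until database lock. Precision falls slightly (SD about 0.26 against 0.22), and the result depends on model form, as the step example shows.
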